## 17.3 Days 8-14 (Open-Label, Continuation Treatment)

Safety and effectiveness endpoints for Days 8-14 will be summarized by randomized treatment group.

**17.3.1 Assessment of Effectiveness**

Summary statistics will be provided by treatment day (overall and by gender) for:

- SOWS-Gossop;
- OOWS-Handelsman;
- MCGI (Subject and Rater);
- VAS-E; and
- COWS.

In addition, the following will be summarized overall and by gender over Days 8-14:

- Duration of exposure;
- Number and proportion of subjects successfully completing detoxification as assessed by the Site Investigator;
- Distribution of number of days required to complete detoxification as assessed by the Site Investigator;
- Average daily dose of lofexidine; and
- Concomitant medications.

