## 14.6 Concomitant Therapy

If the subject is admitted to the inpatient study unit the day before Baseline (i.e., Day -1), a single dose of a short-acting opioid (e.g., morphine) may be administered if needed to keep the subject reasonably comfortable; however, the administration may not occur after 8 PM on Day -1.

The concomitant medications or therapies listed below are permitted during Days 1-7 and Days 8-14 of the study.

1. Multivitamins ( $\leq 1$  tablet orally, administered daily at 9 AM).
2. Guaifenesin (for cough) ( $\leq 2$  teaspoons orally every 2 hours, as needed [PRN]).
3. Alumina, Magnesia, and Simethicone (for emesis and nausea) ( $\leq 30$  mL orally every 4 hours, PRN).
4. Dioctyl sodium sulfosuccinate (for constipation) ( $\leq 100$  mg orally every 8 hours, PRN).
5. Psyllium hydrocolloid suspension (for constipation) ( $\leq 1$  tablespoon orally every 12 hours, PRN).
6. Bismuth sulfate (Pepto-Bismol®) (for diarrhea) ( $\leq 6$  doses of 30 mL orally every 24 hours, PRN).
7. Acetaminophen (for headache, muscle aches, or other discomfort) ( $\leq 4$  doses of  $\leq 650$  mg orally every 24 hours).
8. Zolpidem (for insomnia) ( $\leq 10$  mg orally, PRN, may repeat 1 time if administered before 5:00 AM (i.e., 3 hours before the first morning dose of lofexidine or placebo). Zolpidem must not be administered before 11:00 PM (which is the time of the last daily dose of lofexidine or placebo).
  - 8a. Note: A short-acting benzodiazepine (e.g., oxazepam) may be used ad libitum for insomnia during the second part of the study (i.e., Days 8-14).
9. Nicotine replacement therapy (patch, inhaler, gum, nasal spray).

All other medications must be approved by the Sponsor's Medical Monitor before administration. If a subject requires any other medication for intolerable nausea and emesis (including a prescription opioid or non-opioid or an over-the-counter opioid or non-opioid) other than alumina, magnesia and simethicone, the subject will be discontinued from the study and given appropriate treatment according to the standard of care (see [Section 14.5.1](#)).

All medications taken will be recorded in the subject's source document and eCRF along with dose, dates of administration, and reason for use.

Psychosocial therapy (e.g., art, music, group sessions) will be allowed per standard of care at individual study sites. Acupuncture, however, will not be allowed. All therapies will be recorded in the subject's source document and eCRF.

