Time to removal from study treatment is defined as the last study day on which the subject received treatment. The time for subjects who complete some but not all treatment on Day 7 will be Day 7, uncensored. Subjects who complete all treatments on Day 7 will be censored at Day 7. This endpoint will be summarized descriptively for each combination of treatment group and gender with Kaplan-Meier curves and tabulations of the number and percentage of subjects newly removed from receiving study treatment on each of study Days 1 to 7. Each Lofexidine dose group will be compared inferentially to placebo with a Cox proportional hazards regression model of time to removal from study, including covariates for treatment, gender and site. If the Cox proportional hazards model does not converge, then the covariates gender and site will be dropped from the model and the Cox proportional hazards regression model will be stratified by gender and site instead. The estimated hazards ratio will be reported as a descriptive measure along with the associated 95% confidence interval.

Concomitant Medication Analysis

For each of Days 1 to 7, each subject's number of concomitant medication taken will be treated as a continuous variable. Descriptive statistics will be provided on the as-observed data on each study day and also overall study days.

Status of Detoxification on Day 7 or Early Termination as Assessed by the Site Investigator

Descriptive statistics (numbers and percentages) on the status of detoxification (successful/unsuccessful) as assessed by the Site Investigator at Day 7 or early termination will be presented by treatment group overall and by gender within treatment group.

COWS AUC (1-7)

COWS AUC (1-7) will also be analyzed using a modelling approach analogous to the modelling of SOWS-Gossop AUC (1-7). While the functional form of the time course for SOWS-Gossop is based on historical data, the functional form of the time course for COWS will be based on the data from this study.

In addition, COWS will be analyzed using a mixed model repeated measures (MMRM) model in the same way as detailed for the sensitivity analysis of the primary endpoint with baseline COWS (based on same functional form for primary analysis) as a covariate.

Assessment of effectiveness

Summary statistics will be provided by treatment day (overall and by gender) over days 8-14 (Open Label Phase):

- SOWS-Gossop
- OOWS-Handelsman
- MCGI (Subject and Rater)
- VAS-E

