Effective: 14-Feb-13

Page 17 of 26

• COWS

In addition, the following will be summarized overall and by gender over Days 8-14:

• Number and proportion of subjects successfully completing detoxification and the number of days required to complete detoxification as assessed by the Site Investigator.

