The following will be summarized and analyzed separately for the double blind and open label study phases:

- 1. To assess safety:
 - a. **Suicidality:** The number and percentage of subjects reporting any suicidal ideation or behavior throughout the assessment period.
 - b. **Suicidal behavior only:** The number and percentage of subjects reporting any type of suicidal behavior throughout assessment period.
 - c. **Suicidal ideation only:** The number and percentage of subjects reporting any type of suicidal ideation throughout assessment period.

In addition, taking into account baseline data regarding suicidal ideation to determine if suicidal ideation or behavior has worsened:

d. **Emergence of suicidal ideation:** The number and percentage of subjects reporting no suicidal ideation at baseline and any type of ideation during the assessment period.

Effective: 14-Feb-13

Page 21 of 26

- e. Emergence of serious suicidal ideation: The number and percentage of subjects reporting no suicidal ideation at baseline and had serious suicidal ideation (as defined above; score of 4 or 5 on suicidal ideation severity rating) during the assessment period.
- f. **Worsening of suicidal ideation:** The number and percentage of subjects whose most severe suicidal ideation rating is more severe than it was at baseline.
- g. **Emergence of suicidal behavior:** The number and percentage of subjects who had no suicidal behavior at baseline and any type of behavior during the assessment period.

For each of the above endpoints a-g, Fisher's Exact test will be used to test for a difference between the 2 Lofexidine treatment groups and placebo during the double blind phase only.

Physical Examination

The body systems within the physical examination data at screening, baseline (day 1), day 7 and end of the study will be summarized by treatment (Normal; Abnormal NCS, Abnormal CS). The changes from baseline to end of the study in bodyweight will also be tabulated.

Concomitant medications

Concomitant medication verbatim terms (as recorded on the CRFs) after the initial dose of study drug will be mapped to Anatomical Therapeutic Chemical (ATC) Level 2 and Drug Reference Names using the World Health Organization (WHO) dictionary (Version 3.13 Enhanced) and tabulated by treatment group and overall.

Psychosocial Therapy Sessions

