Only days when the patient was taking active treatment will be considered. Days after active administration will be disregarded.

For the calculation of the daily number of medications taken, the number of distinct coded drug names via the WHO dictionary will be used rather than verbatim terms.

Justification

To make the definitions within this analysis clearer.

Change 14

Section 6.13 Safety analysis

Add the text in bold

All subjects who receive at least dose one of study medication will be included in the analysis of safety.

Safety measures will be summarized for the following subject cohorts for the open label phase:

- \neq All treated subjects;
- ≠ Treated subjects without urinary evidence of illicit drug use (i.e. any positive result in the urine drug screen during the open-label phase, including all categories); and
- ≠ Treated subjects with urinary evidence of illicit drug use (may be further subdivided by type of illicit drug used).

Safety measures will only be summarized for all treated subjects for the double blind phase.

Extent of exposure

Extent of exposure will be described by whether the subject took the trial medication and the number of days exposure to double-blind study medication (last date of double-blind medication minus first date of double-blind medication + 1). Average daily dose of double-blind study

Effective: 24-Dec-2014

Page 13 of 29

medication will also be calculated **by number of doses/exposure (days)**. Exposure to open-label medication will also be calculated as last date of open-label medication – first date of open-label medication + 1. No allowance will be made for breaks in therapy in the exposure calculations. Average daily dose of open-label study medication will also be calculated. If the date of last dosing is completely missing for the trial medication then the date of last dosing will be taken for analysis purposes as the date the medication was last dispensed. As there are no open-label dosing dates recorded on the eCRF, dates of visits will be used instead. In particular it will be assumed that open-label dosing starts one day after double-blind dosing ceases.

Justification

To make the definitions clearer.

Change 15

Section 6.13 Safety analysis

Vital Signs During the Double-Blind Phase

The following text was amended:

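### The SAP omits, without declaring it, the Days 8–14 concomitant-medication summary that protocol 17.3.1 requires, and its by-drug tabulation states no phase split

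*Protocol*

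**What the plan says.** **Protocol.** Section 17.3.1 states that "the following will be summarized overall and by gender over Days 8-14" and names five items, the last being concomitant medications. Section 17.3 adds: "Safety and effectiveness endpoints for Days 8-14 will be summarized by randomized treatment group". The synopsis also lists concomitant medications as a tertiary/exploratory endpoint for Days 8–14.

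**SAP, Days 8–14.** The effectiveness part of SAP 6.11 keeps the five rating scales by day, overall and by gender. Beyond these it lists one further item: "Number and proportion of subjects successfully completing detoxification and the number of days required to complete detoxification as assessed by the Site Investigator". Duration of exposure and average daily dose are not in that list, but they reappear under extent of exposure in 6.13.

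**SAP, Days 1–7.** SAP 6.11 has a separate analysis: "For each of Days 1 to 7, each subject's number of concomitant medication taken will be treated as a continuous variable". Addendum 1 Change 13 bases the count on distinct WHO-coded drug names and adds: "Only days when the patient was taking active treatment will be considered".

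**SAP, by-drug tabulation.** SAP 6.13 says: "Concomitant medication verbatim terms (as recorded on the CRFs) after the initial dose of study drug will be mapped" to dictionary terms and "tabulated by treatment group and overall".

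**Declared changes.** SAP 6.14 lists departures from the protocol analyses. It does not mention the Days 8–14 medication summary, and neither do Addenda 1 and 2.

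**The concern.** An exploratory endpoint that the protocol lists would go unreported in the required form, with nothing on record to say that it was dropped or why.

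The tabulation that remains is a poor substitute. Its window opens at the first dose and has no stated close, so it covers two phases with different rules. Entry to Days 8–14 is limited to those who meet the completer definition (protocol 14.3.4), and the trial's hypothesis is that lofexidine produces more completers. Protocol 14.6 item 8a permits a short-acting benzodiazepine for insomnia in the second part only. If completion differs by arm, the columns of a pooled table differ in follow-up time and in permitted drugs, even when use on any given day is the same. All completers, including those randomized to placebo, are eligible for open-label lofexidine. The placebo column could therefore contain drugs taken during lofexidine treatment. A reader could take a difference in that table for a treatment effect.

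**Working it through.** No sample size, power or alpha figure is involved, so there is no plan figure to reproduce. The check is a comparison of the texts, followed by an illustration of size.

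**Step 1: required against planned.**

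| Item for Days 8–14 (protocol 17.3.1) | Where the SAP puts it |
|---|---|
| Five rating scales by day, overall and by gender | 6.11 |
| Duration of exposure | 6.13, extent of exposure |
| Detoxification completed; days required | 6.11, overall and by gender |
| Average daily dose | 6.13, extent of exposure |
| Concomitant medications, overall and by gender | No Days 8–14 summary; 6.13 tabulates from first dose by arm and overall |

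Only the last row has no phase-specific counterpart.

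**Step 2: is the phase implied elsewhere in 6.13?** Adverse events, laboratory tests, vital signs, C-SSRS and psychosocial therapy each state their phase in their own text. The medication paragraph does not.

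**Step 3: how far could unequal follow-up move a pooled any-use percentage?** The documents give none of the inputs, so these are assumptions: a daily chance q of first use, identical in all arms; a share c completing Days 1–7; 3 days on study for early leavers; 14 days for completers.

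P(any use) = c·[1 − (1 − q)^14] + (1 − c)·[1 − (1 − q)^3]

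With q = 0.05, 1 − 0.95^14 = 0.512 and 1 − 0.95^3 = 0.143.

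- c = 0.30 (placebo): 0.30 × 0.512 + 0.70 × 0.143 = 0.254
- c = 0.50 (lofexidine): 0.50 × 0.512 + 0.50 × 0.143 = 0.327

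| q | c = 30% | c = 50% | Gap (points) |
|---|---|---|---|
| 0.02 | 11.5% | 15.3% | 3.8 |
| 0.05 | 25.4% | 32.7% | 7.3 |
| 0.10 | 42.1% | 52.1% | 10.0 |
| 0.20 | 62.8% | 72.2% | 9.4 |

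With c = 30% in both arms and q = 0.05, both show 25.4% and the gap is zero.

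**Step 4: a drug class permitted only in Days 8–14.** The pooled percentage is the entry proportion times use among entrants. If 50% and 35% enter and 30% of entrants in each arm use the drug, the table shows 0.50 × 0.30 = 15.0% against 0.35 × 0.30 = 10.5%, a gap of 4.5 points. The range is 3.0 points (0.45 × 0.20 − 0.30 × 0.20) to 7.5 points (0.60 × 0.50 − 0.45 × 0.50).

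**Step 5: can the direction reverse?** Let early leavers have a chance r of a recorded rescue drug after removal. Keep q = 0.05 and take c = 30% for placebo and 45% for lofexidine. The early-leaver term becomes (1 − c)·[1 − 0.95^3·(1 − r)].

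| r | Placebo | Lofexidine |
|---|---|---|
| 0 | 25.4% | 30.9% |
| 0.4 | 49.4% | 49.8% |
| 0.6 | 61.4% | 59.2% |
| 0.8 | 73.4% | 68.6% |

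The excess moves from lofexidine to placebo as r rises.

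**Step 6: does a phase split remove the effect?** Restricting Step 3 to Days 1–7 (7 days for completers, q = 0.05, c = 30% against 50%) gives 19.0% against 22.2%. The gap shrinks from 7.3 to 3.2 points but remains, because any-use percentages still depend on days on treatment.

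**The case against.** The strongest reply has four parts.

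- **SAP 6.13 may already split by phase.** Its opening provides separate safety summaries for the open-label and double-blind phases, and the paragraph on medications never says that there is a single table. The content of the table list in Addendum 2 is not visible. This stands in part: a single pooled table is an inference. Against it, that opening follows protocol 17.3.2, whose safety list does not include concomitant medications, and neither does 17.2.11. Even on the generous reading, the gender split is still missing.
- **The blinded phase is covered.** A reader might infer that the plan has no clean medication comparison for Days 1–7. The documents do not support that. The 6.11 analysis with Change 13 is coded, daily and confined to treatment days, so open-label time cannot affect it. It does not show which drugs were taken, and it says nothing about Days 8–14.
- **The direction is unknown.** It is tempting to conclude that longer stay on lofexidine will appear as heavier medication use. That needs unequal completion, which is only hypothesised, and Step 5 shows that it can reverse.
- **Post-exit opioid treatment may not enter the table.** A reader might infer that it will load the placebo column. Protocol 14.5.1 mentions rescue opioids and referral for subjects removed because of adverse events, not for all early leavers. Protocol 15.6.2 speaks of medications taken during study participation, and program entry has its own Day 30 tabulation. Step 5 is therefore a sensitivity run, not a prediction.

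**Conclusion.** The omission is real: a summary required by protocol 17.3.1 is absent from the SAP, and its absence is not declared. The 6.13 tabulation, read as written, would not replace it, because it mixes two phases that differ in who is present and in which drugs are permitted.

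The possible distortion is about 4 to 10 points in any-use percentages under the assumed 30% against 50% completion, and 3.0 to 7.5 points for a drug class confined to Days 8–14. It is zero with equal completion, and its sign is not fixed. All of these figures rest on assumed completion, daily use and length of stay.

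Severity is minor. The endpoint is exploratory and the table descriptive. None of the four comparisons in the testing sequence is affected.

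**What to change.** In SAP 6.13, split the coded concomitant-medication table by phase:

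1. **Double-blind:** first to last double-blind dose, Safety population.
2. **Open-label:** subjects who entered Days 8–14, by randomized group, overall and by gender. Addendum 1 Change 14 notes that the eCRF holds no open-label dosing dates, so the window should follow its convention: open-label dosing starts the day after double-blind dosing ceases, and visit dates stand in for dosing dates.
3. **After the last study dose:** list newly started drugs separately.

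Show days of exposure beside each table, since Step 6 shows that a split alone does not equalise time on treatment. If the sponsor prefers not to produce the Days 8–14 summary, its omission should be declared with a reason alongside the other departures in 6.14.

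The cost is a few lines of SAP text, one further table and a listing. Protocol 14.6 already requires dates of administration for every medication, so no new data are needed.

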**17.3.2 Assessment of Safety**

Safety measures will be summarized for the following subject cohorts:

- All treated subjects;
- Treated subjects without urinary evidence of illicit drug use; and
- Treated subjects with urinary evidence of illicit drug use (may be further subdivided by type of illicit drug used).

Descriptive statistics will be provided for:

- All AEs;
- New onset AEs (including those observed during Days 1-7 whose severity during Days 8-14 is greater than observed during Days 1-7);
- Vital signs;
- ECGs;
- Clinical laboratory tests;
- Physical examinations; and
- C-SSRS.

## 18 DATA MANAGEMENT AND CASE REPORT FORMS (CRFs)

Data management activities and statistical analytical support will be coordinated through the CRO ( ). The CRO will be responsible for the construction and accuracy of the study database.

### 18.1 Data Collection

Data will be collected at the study sites on source documents, which will be entered at the site into electronic CRFs (eCRFs). The eCRFs will be supplied by the CRO ( ). CRFs are to be completed on an ongoing basis during the study. The medical chart and the source documents are the source of verification of data. CRFs should be completed according to the instructions in the study operations manual.

The Site Investigator is responsible for maintaining accurate, complete, and up-to-date records for each subject. The Site Investigator is also responsible for maintaining any source documentation related to the study, including any films, lab reports, or ECG tracings.

Data generated by this study must be available for inspection by representatives of the US FDA, the Sponsor (USWM), the Sponsor representatives, the central IRB and the site's IRB.

### 18.2 Electronic Data Capture

Data entered by site personnel into the electronic data capture (EDC) system will be reviewed by the CRO ( ). If incomplete or inaccurate data are found, a query in the EDC system will be generated for response by the clinical site. Sites will promptly resolve data inconsistencies and errors. An audit trail of any corrections or changes to the data in the EDC system will be maintained. USWM will receive reports at least monthly regarding the quality and quantity of data submitted to the CRO.

Site Investigators agree to routine data audits by the staff of USWM. USWM monitors will routinely visit each site to assure that data entered in the EDC system are in agreement with source documents at the sites. The monitors will also verify that investigational agents have been properly stored and accounted for, subject informed consent for study participation has been obtained and documented in the subject's progress notes, all essential documents required by GCP regulations are on file, and sites are conducting the study according to the research protocol.

### 18.3 Data Analysis

When the study is completed, all data have been entered into the clinical database, and the final database has been locked, statistical analysis of the data will be performed by the CRO's ( ) statisticians or an independent statistician in accordance with the Analytical Plan of this protocol (see [Section 17](#)) and detailed in the SAP. Periodically, during the investigation, the CRO will also prepare summary reports of the data, with no identification or grouping by randomized treatment, so that progress of the study can be monitored. Various reports will be prepared for USWM and others, as appropriate.

## **18.4 Study Documentation and Records Retention**

Study documentation includes all eCRFs, data correction forms, workbooks, source documents, monitoring logs and appointment schedules, sponsor-investigator correspondence and regulatory documents (e.g., signed protocol and amendments, IRB correspondence and approved consent form and signed informed consent forms, Statement of Investigator form, and clinical supplies receipt and distribution records).

Source documents include all recordings of observations or notations of clinical activities and all reports and records necessary for the evaluation and reconstruction of the clinical research study. Accordingly, source documents include, but are not limited to, laboratory reports, ECG tracings, x-rays, radiologist reports, subject diaries, biopsy reports, ultrasound photographs, subject progress notes, hospital charts or pharmacy records, and any other similar reports or records of any procedure performed in accordance with the protocol. Whenever possible, the original recording of an observation should be retained as the source document; however, a photocopy is acceptable provided that it is a clear, legible, and exact duplication of the original document. Any duplicate of a source document to be retained as a part of a eCRF should maintain subject confidentiality per HIPAA.

Government agency regulations and directives require that the investigator must retain all study documentation pertaining to the conduct of a clinical trial. These documents must be kept for a minimum of 2 years after the approval of a new drug application (NDA) and finalization of all marketing strategies, or if the NDA is not approved, for 2 years after discontinuation of the IND, whichever is the later. In all instances sites must get permission from USWM before disposition of any study documentation and materials.

